Although we are not controlling the ventilatory strategy in both groups, physicians are encouraged to comply with the following ventilator strategy: tidal volume (Vt) of 4 - 6mL/kg of predicted body weight, a plateau pressure < 30cmH₂O, driving pressure < 15cmH₂O, respiratory rate to maintain arterial pH > 7.2 and fraction of inspired oxygen (FiO₂) and positive end-expiratory pressure (PEEP) to keep oxygen saturation (SpO₂) ≥ 88% or partial pressure of oxygen (PaO₂) ≥ 55mmHg. Sedation drugs and the use of other strategies for ARDS management such as use of neuromuscular blocking agents, prone positioning, nitric oxide and extracorporeal membrane oxygenation (ECMO) are left to physicians' discretion and are registered daily on the study's electronic case report form (eCRF). Each center is encouraged to follow institutional guidelines for liberation of mechanical ventilation. The study timeline is shown in figure 2.

Procedure to COVID-19 diagnosis

Due to the possibility of false negative tests, especially on the first days of symptoms,⁽²¹⁾ associated with different sensitivities depending of the site of collection, patients with negative laboratory tests included in the study are evaluated by a blinded committee formed by two critical care physicians of the research group with experience treating COVID-19 patients (Adjudication Committee). This committee will take into account the timing of testing, clinical symptoms and analysis of chest image (computed tomography scan of the lungs, or chest X-ray) to define if the patients has COVID-19 infection with negative laboratory tests (probable COVID-19 infection) or if the patient possibly has not COVID-19 infection. Patients with positive polymerase chain reaction (PCR) tests for SARS-CoV2 are deemed to have confirmed COVID-19 infection.

The main analysis will be based on the intention-to-treat principle, with additional sensitivity analysis regarding the COVID-19 infection status (confirmed vs not confirmed).

Adverse events

The most common adverse effects of corticosteroids use are hyperglycemia and possible increase in infections rates. Data on glycemic control is collected daily until day 14 and data on the development of new infections is collected daily until day 28. For any other adverse events a specific form is available on the eCRF and the data is sent in real time to the coordinating center.

Handling of protocol deviations

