Adherence to protocol and corticosteroids use in both groups is accessed daily. The use of corticosteroids in the control group is not forbidden since critically ill patients might have another

indication for corticosteroid use during their ICU stay. However, any use of corticosteroids for treating ARDS and or refractory hypoxemia in the control group is considered protocol deviation. Changes in dosage of dexamethasone or early interruption in the intervention group will also be considered protocol deviation.

If during the trial the patient is deemed to not have COVID-19 infection, which is defined by a negative laboratory tests along with negative evaluation by the Adjudication Committee, the study drug will be stopped, data on these patients will be collected until day 28 and will be included in the final analysis. However, giving the epidemiological context and inclusion criteria, it is expected that only a minority of patients will be in this group.

All centers will receive an initial training session before initiating recruitment to ensure consistency of the study procedures and data collection.

Data collection and management

Unidentified patient data will be collected through an electronic online data capture tool (REDCap).^(22,23) Demographic and baseline data, height, Simplified Acute Physiology Score (SAPS) 3, use of corticosteroids prior the randomization, and the HScore for diagnosis of secondary hemophagocytic lymphohistiocytosis (Table 3) are collected for all patients. The SOFA score is collected on days 1, 2, 3 and 7. Data from gas exchange, lung mechanics, hemodynamic, laboratory data, use of neuromuscular blocking agents, prone positioning and use of ECMO are collected prior randomization and until day 14.

The use of mechanical ventilation or any other ventilation/oxygen support (high flow nasal cannula, non-invasive ventilation, use of supplementary oxygen) and data on the 6-point Ordinal Scale (Table 1) are collected daily until day 28 or until hospital discharge whichever comes first. Vital status at ICU and hospital discharge and any other relevant clinical data such as nosocomial infections, insulin use for glycemic control, antibiotic use, and other therapies for COVID-19 (hydroxychloroquine, chloroquine and azithromycin) are collected.

Data on mechanical ventilation are collected in specific forms with data on date and time of initiation and discontinuation of therapy.

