We will use the Haybittle–Peto boundary stopping rule for both safety and efficacy based on the evidence of significant differences between intervention or control group regarding ventilator free days at day 28, mortality or adverse events. The stopping rule for safety will be a p-value <0.01 and for efficacy p-value <0.001 . The Haybittle–Peto boundary is a conservative stopping rule at interim analysis that has minimal impact in increasing type I error in two-arm trials⁵. We will not adjust the final tests for sequential analysis. The interim analyses will be performed by an external and independent DMC.

Basic reporting principles:

The baseline characteristics of the patients will be displayed as the supplementary table 1 (**Table 1S**):

Table 1S - Baseline characteristics of included patients

	Dexamethasone (Dex.) n = xxx	Control (Cont.) n = xxx
Age, mean (SD)	xx.x ± xx.x	xx.x ± xx.x
Female sex, N (%)	xx.x (xx.x)	xx.x (xx.x)
SAPS3 score, mean (SD)	xx.x (xx.x)	xx.x (xx.x)
Number of non-pulmonary organ failures, median [IQR]	x.xx [x.xx - x.xx]	x.xx [x.xx - x.xx]
Time since onset of symptoms, median [IQR], days	x.xx [x.xx - x.xx]	x.xx [x.xx - x.xx]
Days intubated prior to randomization, median [IQR]	x.xx [x.xx - x.xx]	x.xx [x.xx - x.xx]
COVID-19, N (%)		
Positive	xx.x (xx.x)	xx.x (xx.x)
Negative	xx.x (xx.x)	xx.x (xx.x)
In analysis	xx.x (xx.x)	xx.x (xx.x)
Not collected/unavailable	xx.x (xx.x)	xx.x (xx.x)
Comorbidities, N (%)		
Hypertension	xx.x (xx.x)	xx.x (xx.x)
Diabetes	xx.x (xx.x)	xx.x (xx.x)
Former smoker	xx.x (xx.x)	xx.x (xx.x)
Active smoker	xx.x (xx.x)	xx.x (xx.x)
Obesity	xx.x (xx.x)	xx.x (xx.x)
Solid tumor	xx.x (xx.x)	xx.x (xx.x)
Hematologic malignancy	xx.x (xx.x)	xx.x (xx.x)
Heart failure	xx.x (xx.x)	xx.x (xx.x)
COPD	xx.x (xx.x)	xx.x (xx.x)
AIDS	xx.x (xx.x)	xx.x (xx.x)
Chronic renal failure	xx.x (xx.x)	xx.x (xx.x)
Chronic dialysis	xx.x (xx.x)	xx.x (xx.x)
Cirrhosis	xx.x (xx.x)	xx.x (xx.x)
Asthma	xx.x (xx.x)	xx.x (xx.x)
Neuromuscular disease	xx.x (xx.x)	xx.x (xx.x)
Previous MI	xx.x (xx.x)	xx.x (xx.x)
Clinical characteristics		
Systolic BP, mmHg, mean (SD)	xx.x ± xx.x	xx.x ± xx.x
Diastolic BP, mmHg, mean (SD)	xx.x ± xx.x	xx.x ± xx.x
HR, bpm, mean (SD)	xx.x ± xx.x	xx.x ± xx.x
SpO ₂ , %, mean (SD)	xx.x ± xx.x	xx.x ± xx.x
HScore ≥169, N ₀ (%)	xx.x (xx.x)	xx.x (xx.x)
Respiratory measures (mean, SD)		
PaO ₂ /FiO ₂	xx.x ± xx.x	xx.x ± xx.x
Tidal volume, mL/kg predicted body weight	xx.x ± xx.x	xx.x ± xx.x

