The primary objective is to evaluate the effectiveness of early intravenous (IV) dexamethasone administration in ventilator-free days at 28 days after randomization, defined as alive and free from mechanical ventilation in adult patients with moderate or severe ARDS due to confirmed or probable SARS-CoV2 infection. Patients discharged from the hospital alive before 28 days will be considered alive and free from mechanical ventilation at day 28. Number of days free from mechanical ventilation will be presented as mean and standard deviation. The treatment effect will be presented as mean difference, with 95% confidence interval and P-value. We will use a generalized linear model with beta-binomial distribution or zero/one inflated beta distribution, with center as random effect and adjusted for age, corticosteroid use before randomization and PaO₂/FiO₂ ratio.

All-cause mortality rates at 28 days will be analyzed using a mixed Cox model, with centers as random effects (frailty model). The treatment effect on SOFA Score 48h, 72h, and 7 days after randomization will be analyzed by a linear mixed model with centers as random effects. For the clinical status of patients, an ordinal logistic regression will be used. The results will be presented as a proportional odds ratio comparing two combinations: Intervention versus Control. The probability ratios will be derived from a mixed logistic regression of proportional probabilities adjusted for age and PaO₂/FiO₂ ratio, with random intercepts for the center. The cumulative ordinal scores will be presented separately, as well as the main secondary results. Each odds ratio will be estimated using mixed logistic regression. The same models will be used to compare the effects of treatment on the follow-up. In case of the proportional odds assumption is not met, categories of the Ordinal scale 1-4 will be grouped as a single category for the analysis. All secondary outcomes are exploratory and no adjustment for multiple testing will be made.

Adverse events will be expressed as counts and percentages and compared between groups using the Chi-square test. The main results will be displayed as the supplementary table 2 (**Table 2S**). The significance level for all analyses will be 0.05. There will be no adjustment for multiple testing. All analyses will be performed using the R software⁶ (R Core Team, Vienna, Austria, 2020).

Table 2S - Main results presentation

Outcomes	Dex.	Cont.	Treatment effect	

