	n = xxx	n = xxx	Dex. versus Cont. [IC95%]	p valor
Primary outcome				
Ventilator free days from 1 to 28 d, mean (SD)	xx.x ± xx.x	xx.x ± xx.x	x.xx [x.xx; x.xx]	x.xx
Secondary outcomes				
Clinical status at day 15, N (%)				
Category 1 - 5 versus 6 (alive vs dead)	x.xx (x.xx)	x.xx (x.xx)	x.xx [x.xx; x.xx]	x.xx
Category 1 - 4 versus 5 - 6	x.xx (x.xx)	x.xx (x.xx)	x.xx [x.xx; x.xx]	x.xx
Category 1 - 3 versus 4 - 6	x.xx (x.xx)	x.xx (x.xx)	x.xx [x.xx; x.xx]	x.xx
Category 1 - 2 versus 3 - 6	x.xx (x.xx)	x.xx (x.xx)	x.xx [x.xx; x.xx]	x.xx
Category 1 versus 2 to 6 (at home versus hospital or dead)	x.xx (x.xx)	x.xx (x.xx)	x.xx [x.xx; x.xx]	x.xx
All-cause mortality at 28 days	x.xx (x.xx)	x.xx (x.xx)	x.xx [x.xx; x.xx]	x.xx
Number of days of MV from 1 to 28 d	x.xx (x.xx)	x.xx (x.xx)	x.xx [x.xx; x.xx]	x.xx
ICU free days at 28 days	x.xx (x.xx)	x.xx (x.xx)	x.xx [x.xx; x.xx]	x.xx
SOFA scores				
48 hours	x.xx (x.xx)	x.xx (x.xx)	x.xx [x.xx; x.xx]	x.xx
72 hours	x.xx (x.xx)	x.xx (x.xx)	x.xx [x.xx; x.xx]	x.xx
7 days	x.xx (x.xx)	x.xx (x.xx)	x.xx [x.xx; x.xx]	x.xx
Adverse events				
New diagnosis of infection until day 28, N (%)	x.xx (x.xx)	x.xx (x.xx)	x.xx [x.xx; x.xx]	x.xx
Insulin use for hyperglycemia, N (%)	x.xx (x.xx)	x.xx (x.xx)	x.xx [x.xx; x.xx]	x.xx

Sensitivity analyses

We plan to perform analyses to assess treatment effects on the primary and secondary outcomes considering only patients that received the proposed treatment in the intervention group and patients that not received corticosteroids in the control group (per protocol analysis). Additionally, we will also perform sensitivity analysis for the primary outcome in the following groups:

1. Confirmed COVID-19 infection
2. Confirmed and probable COVID-19 infection
3. Patients which received corticosteroids and patients which did not received corticosteroids (as treated analysis)
4. Patients which received the proposed treatment in the intervention group and patients that not received corticosteroids in the control group (Per protocol analysis)

Subgroup analyses

Will also perform subgroup analysis adding an interaction parameter with group in the main model for (Table 3S):

1. Age, years (< 60 and ≥ 60)
2. PaO₂/FiO₂ ratio, mmHg (≤ 100 and >100)
3. SAPS3, points (< 50 and ≥ 50)
4. Duration of symptoms at randomization, days (≤ 7 and > 7)
5. Duration of moderate / severe ARDS to randomization, hours (≤ 24 hours and > 24 hours to 48 hours)
6. Position at randomization; (prone or supine)
7. HScore (≥ 169 and < 169)

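### The day-28 infection comparison cannot separate a changed infection rate from changed time at risk; a time-at-risk analysis should be added beside it

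*Combined protocol and SAP*

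**What the plan says.** The protocol section on adverse events names "hyperglycemia and possible increase in infections rates" as the most common adverse effects of corticosteroids, and says that "data on the development of new infections is collected daily until day 28".

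The SAP (Appendix 3) gives one method for all adverse events: "Adverse events will be expressed as counts and percentages and compared between groups using the Chi-square test". In Table 2S the infection row is "New diagnosis of infection until day 28, N" (%). It has columns for a treatment effect with 95% interval and a p-value, but the effect measure for adverse events is not named. The sensitivity analyses cover the primary and secondary outcomes only. No rate, person-time, time-to-infection or competing-event analysis of infection is planned.

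Death is handled differently: "All-cause mortality rates at 28 days will be analyzed using a mixed Cox model", with center as a random effect.

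The SAP's interim stopping rule (p<0.01 for safety) rests on differences in "ventilator free days at day 28, mortality or adverse events".

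On available data, the protocol's data collection section says "Data on mechanical ventilation are collected in specific forms with data on date and time of initiation and discontinuation of therapy". Ventilation or oxygen support and the ordinal scale "are collected daily until day 28 or until hospital discharge whichever comes first".

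**The concern.** The chi-square asks whether the same share of patients in each arm is ever diagnosed with an infection by day 28. A patient who dies uninfected on day 3 counts exactly like one observed uninfected for 28 days. If nosocomial infection arises mainly while a patient is alive and ventilated, that share depends on the infection rate and on the length of exposure.

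Exposure is what the trial sets out to change: its hypothesis is more days alive and free of ventilation, it is sized on a gain of three such days, and mortality is a secondary outcome. A difference in the percentage, or its absence, would then have two possible explanations, and the plan has no analysis to tell them apart. Infection is one of the two harms the protocol names and one of only two adverse-event rows in the main results table. What is at stake is the reading of a safety result, not the primary conclusion.

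**Working it through.** **1. The plan's own figures.** No power or expected rate is stated for infection, so the only figure to reproduce is the sample size. Per arm, 2 × 9² × (1.960 + 0.842)² / 3² = 141.3, so 142, or 284 in total against the stated 290. Then 290 × 1.15 × 1.04 = 346.8 against the stated 350. At 1:1 this is 175 per arm.

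**2. A model tied to the plan's 8 and 11 ventilator-free days (VFD).** Let λ, μ and ν be constant daily hazards of infection, death and liberation, with h = μ + ν and no risk of death or infection after liberation.

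- 28-day mortality = (μ/h)(1 − e^(−28h))
- mean VFD = ν[28/h − (1 − e^(−28h))/h²]
- proportion infected = [λ/(λ+h)](1 − e^(−28(λ+h)))

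Assumed, not in the documents: control mortality 50%, control infected 30%.

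- Control: μ = 0.0482 and ν = 0.0401 give mortality 50% and VFD 8.0; λ = 0.0394 gives 30%. Mean ventilated time is (1 − e^(−28h))/h = 10.4 days.
- Equal exposure, rate ratio 1.5: 39.5% infected, chi-square power 46%.
- Whole gain from faster liberation: ν = 0.0630 gives VFD 11 and 8.6 ventilated days. At rate ratio 1.5, λ = 0.0591 and the proportion is (0.0591/0.1704)(1 − e^(−4.77)) = 34.4%. Chi-square power for 30% against 34.4% is 14%. For a cause-specific test, ln 1.5 / √(1/52.5 + 1/60.2) = 2.15, and Φ(2.15 − 1.96) gives about 57%. A rate ratio of 1.23 yields 30% in both arms, so it is fully masked.
- Death hazard 1.3 times higher: at rate ratio 1.5, 36.1% infected and power 23%. A rate ratio of 1.14 is fully masked.

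Across control mortality 30–60% and control infected 20–40%, the liberation-only route masks rate ratios of 1.21–1.24. At rate ratio 1.5 it leaves chi-square power of 12–15%, against 42–69% for the cause-specific test.

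**3. How far this depends on the route** (control infected 30%; control mortality 40–50% except in the last row).

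| Route to VFD 11 | Infection risk after liberation, relative to ventilated | Rate ratio that gives equal percentages | Chi-square power at ratio 1.5 |
|---|---|---|---|
| Liberation only | 0 | 1.23 | 14–15% |
| Liberation only | 25% | 1.08–1.10 | 34–36% |
| Liberation only | 50% | 1.01–1.03 | 48–52% |
| Liberation only | 100% | 0.93–0.96 | 65–67% |
| Liberation and fewer deaths | 0 | 1.02–1.06 | 36–42% |
| Fewer deaths only (control mortality 50–60%) | 0 | 0.59–0.62 | 99% or more |

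In the last row an unchanged rate shows as 30% against 41.5–43.4%. That route needs mortality to fall from 60% to 30%, or from 50% to 3%, so it marks a limit and not an expectation.

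**4. Simulation with a less regular time course.** Assumed: 175 per arm; control mortality 50%; gamma (shape 2) times to death (mean 11 days) and to liberation (mean 16 days), capped at day 28, giving 12.7 mean risk days; infection hazard 2–3% per risk-day. Ranges cover both hazards and post-liberation risk of zero, or of half the ventilated rate up to discharge a mean of 8 days later.

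| Dexamethasone arm, true rate ratio 1.5 | Chi-square power |
|---|---|
| Same exposure | 43–57% |
| Faster liberation (survivor mean 12 days) | 22–37% |
| More, earlier deaths (60%, mean 8 days) | 14–17% |
| Fewer deaths (40%, mean 13 days) | 61–79% |

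A cause-specific test has 41–60% power in the early-death case. With fewer deaths it is the weaker of the two (49–62% against 60–71% with no post-liberation risk).

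With a rate ratio of 1, the chi-square shows significantly fewer infections in 11–17% of trials under early deaths. It shows significant harm in 5–7% when deaths fall and there is no post-liberation risk. Nominal is 2.5% in each direction.

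**The case against.** With follow-up fixed at 28 days, the randomized proportion is a proper cumulative incidence: the patient's total infection risk under each strategy, including any benefit of coming off the ventilator sooner. The documents use the word rates loosely (they also speak of mortality rates at 28 days), so the adverse-event wording does not commit the trial to a hazard question. Table 2S shows mortality, ventilation days and ICU-free days alongside, which gives a reader context. All of this stands, and it is why the chi-square should stay.

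Infection risk need not stop at liberation. This also stands: if half the ventilated rate persists to day 28, simulated chi-square power under faster liberation is 43–51%, close to equal exposure. It does not help when deaths come early, because death ends the risk altogether. Power there stays at 14–15%, and spurious findings of fewer infections rise to 15–19%.

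A Cox model ended at death or discharge is not a complete remedy. If risk stops at liberation, it recovers only 31–41% power in the faster-liberation case, because ventilator-free hospital days remain in the risk set.

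A reader might infer that the interim rule would pass a drug that kills early. The documents do not support that. Mortality is a separate trigger under the same rule. The DMC charter ties its adverse-event threshold to severe events, gives the DMC the whole database, and lets it weigh evidence beyond the fixed limits.

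**Conclusion.** The planned comparison answers the absolute-risk question and leaves the rate question unanswered. Because exposure is expected to differ by arm, its result alone cannot be read as evidence for or against a change in infection rate. The distortion can be large: at a rate ratio of 1.5, power ranges from 14–17% to 61–79% according to what happens to death and liberation.

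A reader might conclude that a real rise in infection will be hidden, or that the test is invalid. Neither follows. Full masking from faster liberation needs a rate ratio near 1.2, the whole benefit coming through liberation, and risk ending there. A rate ratio of 2.0 keeps about 51–66% chi-square power even then. If lives are saved, the percentage overstates the change in rate.

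All sizes rest on assumed mortality, infection hazards, time courses and post-liberation risk, since the documents give none. The direction in each scenario is more secure than the figures. This is a cheap improvement to a safety analysis, not a flaw in the primary one.

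**What to change.** Keep N (%) and the chi-square for new infection to day 28, labelled as the absolute-risk comparison, and name the effect measure shown in Table 2S. Add to the SAP:

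- (a) a cause-specific Cox hazard ratio for first new infection, with center as random effect and follow-up ended at death or hospital discharge, shown with cumulative incidence curves by arm that treat death and discharge as competing events;
- (b) infections per 1,000 ventilator-days by arm, because the model in (a) does not separate ventilated from liberated time.

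In the DMC charter, state that both the absolute-risk and the cause-specific results are supplied when infection is reviewed at the interim analyses.

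The cost is a few lines in the SAP and charter, one more model and one more rate. No new data are needed: infections are recorded daily, ventilation start and stop times are captured, and the planned mortality model already requires dates of death. The downside is that the cause-specific result conditions on survival after randomization, so it must be read together with the day-28 percentage and mortality. The additions should be fixed before database lock.

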- Patients who did use corticosteroids during hospital stay for periods equal or greater than two days
- Use of immunosuppressive drugs
- Cytotoxic chemotherapy in the past 21 days
- Neutropenia due to hematological or solid malignancies with bone marrow invasion
- Patient is expected to die in the next 24 hours
- Consent refusal for participating in the trial

Study protocol

Randomization and allocation concealment

Patients are eligible for enrolment if all the inclusion criteria and none of the exclusion criteria are met. Patients are being randomized in a 1:1 ratio to one of the two groups (Figure 1): standard treatment plus dexamethasone (intervention group) and standard treatment without dexamethasone (control group). The randomization list is generated by an independent statistician in random blocks of 2 and 4 in order to preserve the allocation concealment and is stratified by center. Randomization is performed by an online web-based central, available 24 hours a day. The group treatment is disclosed to the investigator only after all information regarding patient enrolment is recorded in the online system. Patients are screened for enrolment by the principal investigator and the research team at each study center.

Blinding

This is an open-label trial where the investigators, caregivers and patients are not blinded regarding the intervention. All statistical analyses will be performed in a blinded manner with respect to group allocation.

Trial intervention and treatment strategy

Each ICU enrolling patients in the trial are encouraged to follow the best practice guidelines and their institutional protocol for the care of critically ill patients with COVID-19. Laboratory testing, hemodynamic management, ventilatory strategy, antibiotics usage, venous thromboembolism and stress ulcer prophylaxis, along with all other ICU interventions are left at the discretion of the ICU team for both intervention and control group.

Patients in the intervention group are receiving after randomization dexamethasone 20mg intravenously once daily for 5 days, followed by dexamethasone 10mg intravenously once daily for additional 5 days or until ICU discharge, whichever occurs first. Patients in the control group are not receiving dexamethasone.

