Safety and stopping standards	
If there is a general increase in severe adverse events at 28 days with a two-tailed alpha threshold <0.01, the DMC will consider efficacy data together with safety information to consider stopping the study, also the DMC can choose to wait for the next interim analysis for weighting. To do this, the DMC will have access to the entire study database required for this specific intermediate analysis and may request additional data if necessary. If the study is not interrupted after any intermediate analysis, the alpha thresholds for severe adverse events will not be adjusted in the final statistical analysis. The occurrence of other non-severe adverse events (hyperglycemia) will also be weighted by DMC.
 
Additionally, the DMC will consider other factors outside the rigid limits mentioned above to prepare a recommendation on the study. Safety and efficacy findings often need to be weighed along with external evidence outside the rigid limits. We believe that the DMC is free to carry out such consideration and provide its opinion in these terms.

Decision making	
What decisions/recommendations will be open to the DMC	
DMC will recommend one of the following written actions to the Academic Steering Committee:
 
 1. Continue the study according to the protocol and any related changes 2. Modify the study protocol. Modifications may include, but are not with others, changes in inclusion/exclusion criteria, frequency of safety monitoring, changes in study procedures 3. Pause inclusion, with pending resolution of a specified problem 4. Interrupt the study
How decisions or recommendations will be reached within the DMC	
DMC members formally vote on all recommendations to be submitted to the steering committee. To vote, a Member of the DMC must be present at the meetings convened. A simple majority vote of the members transmits a proposal, motion or recommendation to the Academic Steering Committee.

Reporting	
To whom will the DMC report their recommendations / decisions, and in what form	
The DMC will report their recommendations/decisions to the Academic Steering Committee through a letter or e-mail within one week after the DMC meeting. A copy of the DMC recommendation will be stored in the trial master file.

Agreement and potential competing interests form

COVID-19-associated ARDS treated with DEXamethasone: CoDEX Trial

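### Table 2S measures the named harm hyperglycemia only through insulin use, an unblinded treatment decision with no glucose criterion, time window or rule for prior insulin users, and no analysis of the daily glycemic data is planned

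*Combined protocol and SAP*

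**What the plan says.** The protocol's Adverse events section names hyperglycemia and infection as the expected harms and states: "Data on glycemic control is collected daily until day 14". The Data collection section also lists "insulin use for glycemic control" among the recorded items.

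The adverse events block of SAP Table 2S has two rows. The infection row reads "New diagnosis of infection until day 28, N" (%), so it is limited to new events and has an end date. The glycemic row reads "Insulin use for hyperglycemia, N" (%), with neither. The SAP text compares adverse events by chi-square at 0.05 and specifies no analysis of glucose.

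On the setting, the Blinding section says: "This is an open-label trial where the investigators, caregivers and patients are not blinded regarding the intervention". The Trial intervention section names laboratory testing among the items of care that, "along with all other ICU interventions are left at the discretion of the ICU team for both intervention and control group". The documents state no glucose criterion that defines the insulin row.

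Diabetes is a comorbidity row in Table 1S and is not an exclusion criterion. Table 1S has no row for insulin use at baseline. The DMC charter (Safety and stopping standards) adds: "The occurrence of other non-severe adverse events (hyperglycemia) will also be weighted by DMC". It gives no definition of hyperglycemia.

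**The concern.** Whether a patient receives insulin depends on that patient's glucose, on how often it is measured, and on how readily staff treat it. In this trial the staff know the allocation, and both testing and treatment are at their discretion. A difference in the insulin row could therefore reflect the drug, the prescribing, or both, and equal percentages would not show that glucose was equal. The protocol's Discussion defends the primary outcome as objective. That defence does not extend to insulin prescribing.

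The row's definition is a separate matter. Diabetic patients can enroll, and some may already be on insulin. Unlike the infection row, this one does not say that only new use counts. Prior users, if counted, are events in both arms whatever dexamethasone does.

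At stake is the reading of one of the two named harms. The protocol's own benchmark for hyperglycemia is a frequency of hyperglycemia (76% versus 70% in the cited dexamethasone ARDS trial), and an insulin percentage cannot be set beside it.

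**Working it through.** The documents give no expected rate, effect size or power for insulin use, so there is no plan figure to reproduce. The calculations below are illustrations.

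**Inputs from the documents:** 350 patients at 1:1, so 175 per arm; significance level 0.05, taken as two-sided; hyperglycemia 70% (control) and 76% (dexamethasone), as cited in the protocol's Discussion.

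**Assumed inputs:** the share of hyperglycemic patients given insulin; the rates of new insulin use; the share b already on insulin at randomization.

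**Power formula** (two proportions, n per arm, p̄ their mean): Φ[(|p1 − p2| − 1.96·se0)/se1], with se0 = √(2p̄(1 − p̄)/n) and se1 = √((p1(1 − p1) + p2(1 − p2))/n).

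**1. Prescribing can create a difference.** Insulin use = hyperglycemia rate × share treated. Hyperglycemia is 70% in both arms.
- Treated 40% versus 60%: 0.70 × 0.40 = 28% and 0.70 × 0.60 = 42%. Then se0 = √(2 × 0.35 × 0.65/175) = 0.0510 and se1 = √((0.2016 + 0.2436)/175) = 0.0504. So Φ[(0.14 − 0.0999)/0.0504] = Φ(0.79), about 79%.
- Treated 40% versus 50%: 28% and 35%, about 29%.

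Without differential treatment the chance would be 5%.

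**2. Prescribing can hide a difference.** With hyperglycemia 70% in control and 76% on dexamethasone, and 50% and 46% of cases treated: 0.70 × 0.50 = 35.0% and 0.76 × 0.46 = 35.0%. The row shows nothing.

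**3. Counting prior users dilutes.** If a share b in both arms is on insulin at randomization and is counted, the observed rate is b + (1 − b)p. The risk difference becomes (1 − b)(p2 − p1). A true difference of zero stays zero in expectation, so this mechanism cannot by itself create a harm. With new use p = 30% versus 45%, a 15-point difference:

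| b | Rates, all counted | Difference (points) | Power, all counted (175 per arm) | Power, non-users only (n per arm) |
|---|---|---|---|---|
| 0% | 30.0% vs 45.0% | 15.0 | 83% | 83% (175) |
| 10% | 37.0% vs 50.5% | 13.5 | 72% | 79% (158) |
| 20% | 44.0% vs 56.0% | 12.0 | 61% | 74% (140) |
| 35% | 54.5% vs 64.3% | 9.8 | 46% | 65% (114) |

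Check at b = 20%: se0 = √(2 × 0.5 × 0.5/175) = 0.0535, se1 = √(0.4928/175) = 0.0531, and Φ[(0.12 − 0.1048)/0.0531] = Φ(0.29), or 61%.

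**4. What a glucose row could detect.** For 70% versus 76% with 175 per arm: se0 = 0.0475, se1 = 0.0474, and Φ[(0.06 − 0.0930)/0.0474] = Φ(−0.70), about 24%. About 859 per arm would be needed for 80%.

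**The case against.** There are several good arguments for the plan as it stands.

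- **Prior users.** A reader might infer that the row counts everyone already on insulin. The documents do not say so. They are silent, and the words limiting the row to hyperglycemia, under an adverse events heading, could be read as new use only. Chronic insulin for diabetes also treats hyperglycemia, so the wording does not settle the matter either way.
- **The DMC.** A reader might infer that the DMC would never see glucose data. The charter contradicts that: the DMC statistician has unlimited access to the study database, and the DMC may request additional data. What is missing is a planned analysis.
- **Glucose is not a clean substitute.** A peak value, or any value over a threshold, depends on how often unblinded staff test, and insulin lowers it. Power is low on the only rates in the documents (24%). Receiving insulin is a clinically meaningful event in its own right. This argument stands, and it is a reason to add a glucose row and keep the insulin row.
- **Assumed rates.** The treated shares, the new-use rates and b have no source in the documents, and the plan claims no power for any adverse event. This too stands: the figures show direction and possible size and are not predictions.
- **Importance.** The charter classes hyperglycemia as non-severe, and no numeric stopping threshold is tied to it.

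None of this answers the central point. The only planned glycemic comparison is of a discretionary decision by unblinded staff, while the SAP leaves unused the glycemic data that the protocol says are collected.

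**Conclusion.** The point holds as a gap in safety reporting. As planned, the insulin row cannot separate an effect on glucose from a difference in prescribing. That difference can act in either direction: under the assumed treated shares, equal hyperglycemia gives a 29% to 79% chance of a nominally significant result, and a 6-point difference in hyperglycemia can vanish.

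The handling of prior insulin users is unspecified. If they are counted, the loss is small when few patients are on insulin (72% versus 79% power at b = 10%) and larger when many are (46% versus 65% at 35%). It would be wrong to conclude that this mechanism manufactures a harm. In expectation it only dilutes one; an apparent harm needs differential prescribing or a chance imbalance at baseline.

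The existence of the gap rests on the documents alone; its size rests on the assumed rates. The primary analysis, the sample size and the mortality analysis are untouched.

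**What to change.** Before database lock, amend the SAP and the Table 2S shell as follows.

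1. Keep the insulin row, state its time window, and state how patients already on insulin at randomization are handled.
2. Add a glycemia summary by arm from the daily data to day 14, with the measure and any threshold fixed in advance.
3. Add new insulin use among patients not on insulin at randomization, with a stated window.
4. Show the two added rows by baseline diabetes status, which Table 1S already reports.
5. Plan the same rows for the DMC, so that its weighing of hyperglycemia rests on a defined quantity.

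The cost is mainly wording. The documents do not say that the eCRF holds glucose values or insulin status at randomization, so both must be checked first; if either is absent, the matching row cannot be built and the report should say so. The new-use row has a smaller denominator (for example 140 per arm if 20% are prior users). The glucose row is still influenced by discretionary testing and by insulin, and its power is low. The rows should therefore be read together, with none taken as decisive.
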